3 OBJECTIVES AND ENDPOINTS

In this cluster RCT, **we propose to test whether**, compared with using an existing incident reporting system, **implementing the SAFE Loop in acute care nursing units:**

Aim 1: improves incident reporting practices by increasing the rate at which nurses report high-priority medication incidents (H1.1) and the number of contributing factors described per report (H1.2).

Aim 2: improves nurses’ attitudes toward incident reporting, including perceptions of feedback and communication about error (H2.1) and of the frequency with which events are reported (H2.2).

Aim 3: reduces rates of high-priority medication events (H3.1) and high-priority medication events involving harm (H3.2).

OBJECTIVES	ENDPOINTS	JUSTIFICATION FOR ENDPOINTS
Primary		
Aim 1: To determine whether SAFE Loop implementation increases the number of contributing factors described per report (H1.2)	(H1.2) The number of system plus human contributing factors per incident report	Reports including more contributing factors will allow quality improvement personnel to develop solutions that are better-informed
Aim 2: To determine whether SAFE Loop implementation improves nurses’ attitudes toward incident reporting, including perceptions of feedback and communication about error (H2.1)	(H2.1) Hospital Survey on Safety (SOPS) Culture Survey performance on composite measure on “Feedback & Communication About Error”	Nurses involved in SAFE Loop will confirm that an effective safety action loop has been established by scoring higher on measures of feedback/communication about error
Aim 3: To determine whether SAFE Loop implementation reduces rates of high-priority medication events (H3.1)	(H3.1) Rate per 1,000 patient-days of Target Medication Events selected by nursing units in intervention groups	Nursing units involved in the intervention arms will reduce the number of target medication events compared to control group units
Secondary		

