The survey takes 10-15 minutes to complete and includes 42 items used to derive 12 composite measures (**Table 8**), 2 single-item measures, and respondents' backgrounds (unit, staff position, interaction with patients, years of experience in current profession, hospital, and current nursing unit). Most items are scored on a scale from 1 (strongly agree) to 5 (strongly disagree). Creating composite scores involves: (1) inverting the scales of any negatively worded items, (2) identifying positive responses (1 or 2); (3) calculating the percent of responses that were positive for each item (excluding missing values), and (4) averaging the percent positive across all items within a composite measure.

The two composite measures we plan to use are directly relevant to incident reporting and likely to be responsive to system-level changes. *Feedback and Communication About Error* includes three items: staff are informed about errors, discuss ways to prevent errors, and are given feedback about changes implemented. The *Frequency of Events Reported* also includes three items: staff report mistakes that are caught before affecting the patient, with no potential to harm, and that could harm but did not. In a prior analysis from three nursing units at three different hospitals, scores on these two composite measures were correlated ($\rho=0.56$) but factor analyses indicated that they captured distinct concepts (loaded separately). Respectively, Cronbach α values for these measures were 0.77 and 0.78 among nurses, demonstrating good internal consistency.⁵⁵

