9 STATISTICAL CONSIDERATIONS

9.1 STATISTICAL HYPOTHESES

Aim 1 Hypotheses:

1.1 The rate per 1000 patient-days at which nurses report incidents will increase more in nursing units engaged in the SAFE Loop than in units using the existing reporting system.

1.2 The number of system plus human factors per incident report will increase more in nursing units engaged in the SAFE Loop than in units using the existing reporting system. (Primary outcome for Aim 1)

Aim 2 Hypotheses:

2.1 Nurses' perceptions of feedback and communication about error on the nursing unit will improve more in nursing units engaged in the SAFE Loop than in units using the existing reporting system. (Primary outcome for Aim 2)

2.2 Nurses' perceptions of the frequency with which events are reported on the nursing unit will increase more in nursing units engaged in the SAFE Loop than in units using the existing reporting system.

Aim 3 Hypotheses:

3.1 The rate of medication events designated as high priorities will decline more in nursing units engaged in the SAFE Loop than in units using the existing reporting system. (Primary outcome for Aim 3)

3.2 The rate of medication events designated as high priorities and involving harm will decline more in nursing units engaged in the SAFE Loop than in units using the existing reporting system.

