9.3 POPULATIONS FOR ANALYSES

The trial will randomize 20 nursing units to two arms: (1) the SAFE Loop, and (2) the existing reporting system (control). All analyses will compare data between these two arms.

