Assessment of Survey Measurement Properties: To evaluate the two selected composite measures' internal consistency, we will calculate Cronbach's α using data from baseline survey. To assess construct validity and convergent validity, respectively, we will evaluate associations (Pearson correlation coefficients) between scores on the composite measures and: (1) the full Hospital SOPS, and (2) incident reporting rates at the nursing unit level. To assess responsiveness, we will compare scores from baseline and follow-up surveys among nurses in the SAFE Loop arm (paired t-tests). If the composite measures do not demonstrate good internal consistency, construct, and convergent validity, we will use the full Hospital SOPS.

Statistical Analyses: We will compare changes over time between study arms for Feedback and Communication About Error and Frequency of Events Reported. Multivariable Normal regression models will be fitted for both endpoints and we will test hypotheses similarly to Aim 1. We will adjust for nurse characteristics from the AHRQ survey: years working in this hospital, years worked in current nursing unit, and hours worked per week. We will perform subgroup analyses by years of experience in current profession, because experience has been associated with medication error rates.⁵⁹

Aim 3 Analyses:

Descriptive Analysis: We will calculate rates of preventable ADEs and potential ADEs per 1,000 patient-days, both overall and for the Target Medication Events for the Group 1 and 3 nursing units. We will describe the severity of the events, medication classes, errors, clinicians involved, and stages in drug therapy.

Statistical Analysis: We will compare changes over time between study arms for rates of (a) Target Medication Events per 1000 patient-days and (b) harmful Target Medication Events per 1000 patient-days. Multivariable Poisson models will be fitted with response variable as the number of (a) target medication events and (b) harmful medication events, with offset the length of stay divided by 1000

days. We will test hypotheses similarly to under Aim 1. Model covariates will include patient demographics, biological sex, Elixhauser comorbidity index, and insurance payer.

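### The Aim 2 primary composite gives way to the full Hospital SOPS if undefined validity checks fail, one of them resting on 20 units and on a rate that is itself a trial outcome

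*Combined protocol and SAP*

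**What the plan says.** Section 3 lists the Aim 2 primary endpoint as "Hospital Survey on Safety (SOPS) Culture Survey performance on composite measure on" Feedback & Communication About Error. Section 9.1 marks H2.1 as the primary outcome for Aim 2: nurses' "perceptions of feedback and communication about error on the nursing unit will improve more in nursing units engaged in the SAFE Loop" than in control units.

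Section 9.4.2, under the assessment of survey measurement properties, plans three checks that feed a decision:

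- internal consistency by Cronbach's alpha, "using data from baseline survey";
- construct validity by Pearson correlation with the full Hospital SOPS;
- convergent validity by Pearson correlation with "incident reporting rates at the nursing unit level".

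It also plans a responsiveness check (paired t-tests in the SAFE Loop arm), which is not part of the decision. The decision rule is: "If the composite measures do not demonstrate good internal consistency, construct, and convergent validity, we will use the full Hospital SOPS".

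The confirmatory model in the same section names only the two composites: "We will compare changes over time between study arms for Feedback and Communication About Error and Frequency of Events Reported". The Aim 2 power calculation in section 9.2 also covers only those two. Section 8.1 says the survey "includes 42 items used to derive 12 composite measures"; it defines how items are averaged within a composite but not how an overall score is formed. Overall scores otherwise appear in section 9.4.2 only as something to be described.

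**The concern.** A primary endpoint should be fixed before the data that test it are seen. Here it depends on three judgements made on the trial's own data, with no threshold for any of them. Because the conditions are joined by 'and', the good alpha values cited in section 8.1 (0.77 and 0.78) protect against only one of the three failures.

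The convergent check is the weakest link. It has 20 clusters to work with, and reporting rates across emergency, neonatal, obstetric, medical and intensive care units may differ for reasons unrelated to safety culture. The reporting rate is also an Aim 1 outcome: section 9.1 words H1.1 as the rate at which nurses report incidents, and section 3 narrows it to Target Medication Events. Neither correlation is tied to baseline. If follow-up data were used, one aim's outcome would help choose another aim's primary endpoint. Section 6.3 blinds data collection staff, but the plan does not say that whoever applies this rule is blinded.

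At stake are the credibility of the Aim 2 conclusion and its power, if a focused outcome is exchanged for a broader one with no stated scoring or sample-size basis.

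**Working it through.** **Inputs from the documents.** 20 units (section 9.3); 1,980 nurses, 85% eligible, 60% response, composite SD 37%, meaningful difference 8.6 pp (section 9.2, Aim 2); 665 reports per year (section 9.2, Aim 1); 42 items, 12 composites, 3 items in the primary composite (section 8.1).

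**Plan's own figures.**
- Responses per unit: 1980 × 0.85 × 0.60 / 20 = 50.49; the plan states 50.5.
- SD of a discrete uniform on four points 33.3 apart: sqrt((4² − 1)/12) × 33.3 = 37.3; the plan states 37%.
- Reports per unit per six months: 665/20/2 = 16.6, as stated.
- The Aim 2 table of detectable differences (7 to 13 pp) could not be reproduced with the standard variants tried. The point does not depend on it; where used below, its values are taken as printed.

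**How often a real correlation would fail (cut-off assumed, because the plan gives none).** With n = 20, two-sided 5% significance needs |r| >= 2.101/sqrt(2.101² + 18) = 0.444. By the Fisher z approximation, power = P(Z > 1.96 − atanh(ρ) × sqrt(17)):
- ρ = 0.3: 1.96 − 0.3095 × 4.123 = 0.68, power 0.25, failure 75%.
- ρ = 0.5: 1.96 − 0.5493 × 4.123 = −0.30, power 0.62, failure 38%.

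Simulation of 200,000 bivariate-normal samples per value gives:

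| True correlation | Fails 'significant and positive' | Fails r >= 0.3 | Fails r >= 0.5 |
|---|---|---|---|
| 0.3 | 75% | 49% | 83% |
| 0.4 | 57% | 30% | 68% |
| 0.5 | 36% | 14% | 47% |
| 0.6 | 16% | 5% | 25% |

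An observed r of 0.3 has a 95% interval of tanh(0.3095 ± 1.96/4.123), about −0.16 to 0.66.

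**Measurement noise.** With 16.6 reports per unit and Poisson counts, the reliability of the unit rate is CV²/(CV² + 1/16.6), or 0.04/(0.04 + 0.060) = 0.40 at a between-unit CV of 0.20, the top of the plan's grid. The reliability of the unit survey mean at ICC 0.20 is 50.5 × 0.20/(1 + 49.5 × 0.20) = 0.93. A true 0.5 would then be seen as about 0.5 × sqrt(0.40 × 0.93) = 0.30.

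**What the fallback would register (scoring assumed: plain mean of 12 composites).** Shift = 8.6 × k/12, where k composites gain 8.6 pp and the rest do not change:
- k = 1: 0.72 pp
- k = 2: 1.43 pp
- k = 6: 4.3 pp
- k = 12: 8.6 pp

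Weighting by items instead gives 8.6 × 3/42 = 0.61 pp for one composite and 1.23 pp for two.

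**The case against.** Several points on the other side have force.

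- **The fallback is prespecified.** The one check that looks at change in the SAFE Loop arm, responsiveness, is outside the switching sentence. If all three triggers were assessed at baseline, the choice could not depend on the treatment effect. This stands, but the text ties only alpha to baseline, and a baseline-only rule would still let chance decide the endpoint.
- **The full SOPS may move.** A reader might infer that the replacement is a score that barely moves. The documents do not support that. Section 8.1 cites changes of 8.6 pp (range 6.5 to 10.6) in overall SOPS scores linked to practice changes by hospital leaders. SAFE Loop also trains managers in just culture and involves them and safety leaders in mitigation, so spillover to other composites is plausible. The small shifts hold only if the effect stays within the selected composites.
- **The 12-composite average is an assumption.** The plan never defines how the full SOPS would be scored. That is a gap in its own right.
- **The 7 pp comparison is not like with like.** It is tempting to set 0.7 or 1.4 pp against the smallest printed detectable difference, 7 pp. That figure belongs to a three-item composite. A 12-composite mean has a smaller SD, by a factor sqrt((1 + 11ρ)/12); for assumed inter-composite correlations of 0.3 to 0.8, 7 pp becomes about 4.2 to 6.3 pp.
- **The correlation may not use 20 unit means.** Nurse-level scores against unit rates, or unit-periods, are possible readings. There are still only 20 clusters. Nor does the text say whether one or both composites must fail.

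**Conclusion.** The defect stands: the Aim 2 primary endpoint can be replaced on trial data by an undefined test, at an unstated time for two of its three parts, with an outcome that has no scoring rule, model or power calculation. Nothing elsewhere in the protocol repairs this. Confidence in that is high.

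Confidence in the size is medium. A reader might infer a 38-75% chance of a switch. The documents do not give one: that range needs both a p<0.05 criterion and a true correlation between 0.3 and 0.5, and neither is stated. Under r >= 0.3, a true 0.5 fails about 14% of the time. What can be said is that, with 20 units, a genuine moderate correlation can fail several ordinary cut-offs by chance. The loss after a switch is likewise conditional: about 0.7 or 1.4 pp if only one or both selected composites gain 8.6 pp, rising to 4.3 pp if six do and 8.6 pp if all do.

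**What to change.** In section 9.4.2, delete the switching sentence and state that H2.1 (Feedback and Communication About Error) remains the Aim 2 primary endpoint whatever the psychometric results. Report alpha and both correlations descriptively, all from baseline data. Give the full Hospital SOPS as a supportive analysis with a stated scoring rule.

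The cost is a few lines of wording, with no new data. The small downside is that the composite stays primary even if its measurement properties prove weak at this site; the descriptive results would disclose that.

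If the sponsor prefers to keep a fallback, it would need numeric cut-offs, a rule for one versus both composites failing, baseline-only assessment by someone blinded to arm, and a defined and powered replacement. That is more work for little gain.

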B) *Patients:* Cedars-Sinai has 49,000 inpatient, 7,700 observation, and 58,000 emergency department encounters in a typical year, resulting in a total of 294,470 patient-days of care in study nursing units per year. Under Aim 1, incident reports for about 1,663 patients will be analyzed. Under Aim 3, medical records for 1,520 eligible hospitalizations during the SAFE Loop study period will be randomly sampled and analyzed.

Description of Sites/Facilities Enrolling Participants:

20 Cedars-Sinai acute care nursing units in the main Medical Center

Description of Study Intervention:

We will conduct a cluster RCT to compare nursing units that implement the SAFE Loop, a system-level change in incident reporting, with nursing units that continue to use the existing reporting system. The Safety Action Feedback and Engagement (SAFE) Loop has three phases: Engagement, Fact-finding, and Action & Feedback.

Across the three phases, the SAFE Loop has five Key Attributes: (1) obtaining input from nurses on which problems to address; (2) focusing on selected high-priority events, (3) prompting nurses to report the high-priority events for a designated period and write more informative reports; (4) following standardized investigative procedures to integrate information from sources internal and external to CSMC, and (5) providing feedback to nurses about safety problems and mitigation plans. During all phases, the SAFE Loop Team collaborates with frontline nurses and Unit Managers. (See schemata in Section 1.2)

[figure not shown]
Study Duration: 60 months
Participant Duration: 24 weeks

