Non-intercepted (NCC MERP C-D)	A medication error in which the patient received the medication but did not to experience harm.	A patient with a known allergy to an antibiotic receives the drug anyway but does not develop a rash.

*An injury is an unintended consequence of care that negatively affects a patient's health and/or quality of life. † A medication error is an error anywhere in the process of drug ordering, dispensing, administration, and monitoring.

Descriptive Measures: We will characterize event severity/harm (NCC MERP categories), medication class (e.g., cardiovascular, diabetes, etc.), and route of administration (intravenous, oral, etc.). We will classify any errors by stage in drug therapy (ordering, dispensing, administering, monitoring), profession(s) involved (physician, pharmacist, nurse, other), and error types (allergy, drug-disease interaction, drug-drug interaction, drug-lab interaction, duplicate therapy, therapeutic omission, concentration, duration, route/dosage form, dose/frequency/rate, wrong medication, wrong patient, wrong timing, incomplete order).^{5,6,38,61} We will assess which events are Target Medication Events used by Group 1 and 3 nursing units (yes, no; and which unit).

B. Data Collection: The nursing units will implement mitigation plans designed to prevent Target Medication Events toward the end of the SAFE Loop implementation (Section 2B), which means that medication events will not start to fall until after that. Accordingly, we will monitor medication events during a baseline period, the implementation period, and 6-month follow-on period after implementation (Section 3A). To identify medication events, we will randomly sample 1,520 hospitalizations divided equally between the four study groups and the baseline and follow-on periods. (We will exclude the emergency department from Aim 3).

To detect medication events, we will employ the widely accepted Trigger Tool Method by Institute for Healthcare Improvement. It involves two stages: (1) nurses systematically screen medical records for “triggers” (clues that an event occurred) and write synopses of possible events, and (2) physicians review synopses to confirm and classify them. Many studies have used these methods, including studies by Dr. **[name]**.^{5,6,38,61-64}

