⁵ Audigier, V., White, I., Jolani, S. Debray, T., Quartagno, M., Carpenter, J., van Buuren, S. and Resche-Rigon, M. Multiple imputation for multilevel data with continuous and binary variables. Statistical Science 2018;33(2):160-183

⁶ Resche-Rigon, M. and White, I. R. Multiple imputation by chained equations for systematically and sporadically missing multilevel data. Statistical Methods in Medical Research 2018; 27(6): 1634-1649

⁷ White IR, Royston P, Wood AM. Multiple imputation using chained equations: Issues and guidance for practice. Stat Med. 2011 Feb 20;30(4):377-99.

Aim 3:

Table 3 presents the minimum detectable difference in event rates as functions of between-cluster coefficient of variation and implementation trend using a two-sided t-test for Poisson rates with 80% power at 5% significance level. A difference of 0.50 events per 1000 patient days is clinically meaningful, representing the avoidance of 147 events and 116 harmful events per year hospital-wide.

Table 3: Minimum Detectable Difference in Outcome				
Implementation trend	Betw-Cluster Coeff of Variance			
	0.01	0.05	0.10	0.20
3.1 Target Event Rate				
Yes	0.766	0.929	1.292	2.108
No	0.516	0.631	0.886	1.474
3.2 Harmful Event Rate				
Yes	0.322	0.335	0.373	0.486
No	0.220	0.230	0.257	0.340

Qualitative Interviews:

Qualitative methods do not involve statistical tests or rely on calculations of statistical power. Instead, we provide a rationale for the proposed sample size and describe analytical methods.

After SAFE Loop implementation, we will conduct one-on-one in-person interviews with 10 Nursing Unit Managers and 22 frontline nurses. This sample size will enable us to perform purposive sampling to acquire broad representation by randomization block (there are 5 blocks), study group (there are four groups, with five nursing units per group – one from each block; half of the groups receive the intervention), and nursing unit (there are 10 nursing units that will be randomized to the SAFE Loop arm). Thus, we will interview one nurse manger and two nurses from each study nursing unit, about 6 per block, and 16 per group.

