9.4.2 ANALYSIS OF THE PRIMARY EFFICACY ENDPOINT(S)

Aim 1 Analyses:

Descriptive Analysis: We will perform descriptive analyses of reporting practices during the baseline periods and intervention periods, stratified by study arm. We will calculate rates of reported Target Medication Events and total reported medication events per 1000 patient-days (# of reports*1000/# of patient-days). Next, we will calculate the percentages of reported incidents in each NCC MERP category and the percentages of reports for which preventability could be determined. Finally, we will calculate

the number of contributing system, human, and patient factors per report and describe the types of factors reported.

Statistical Analyses: We will compare changes over time between study arms for: (a) rate of incident reports per 1000 patient-days, and (b) number of system plus human factors per report. Multivariable Poisson regression models will be fitted with response variables as (a) number of reports per patient, with offset given by the length of stay divided by 1000; and (b) number of system plus human factors per report. For both models, the main hypothesis is whether there is an interaction between study arm and time period (baseline, post-intervention). Nursing units will be divided between two implementation steps, creating the possibility of an implementation trend. Therefore, a three-way interaction among study arm, time period, and implementation step (Step 1: Group 1 and 2, Step 2: Group 3 and 4) will be tested. If this is statistically significant, results will be presented separately for each implementation step. Otherwise, implementation step will be an additive effect. Random effects will describe nursing units and models will adjust for demographics, Elixhauser comorbidity index, and primary payer (collected under Aim 3). All hypotheses will be two-sided at 5% significance level. Calculations will be performed in R-package, version 3.5.3.

Aim 2 Analyses:

Descriptive Analysis: We will calculate survey response rates, examine respondent characteristics (years worked in current profession, hospital, and current nursing unit and hours worked per week), and describe outcome measures (overall scores and composite measures) during each study period, stratified by study arm.

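### Harmful Target Events (H3.2) inherit the Aim 1 interaction model, but on the plan's implied rates the 1,520 charts give too few harmful events for that test and nowhere near the 80% power shown in Table 3

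*Combined protocol and SAP*

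**What the plan says.** Section 9.1 states H3.2 as a hypothesis about change from baseline: "The rate of medication events designated as high priorities and involving harm will decline more in nursing units engaged in the SAFE Loop" than in control units. Section 3 lists harm as a secondary endpoint.

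Section 9.4.2 (Aim 3) fits Poisson models to (a) Target Medication Events and (b) harmful ones, with a length-of-stay offset, and for both says: "We will test hypotheses similarly to under Aim 1. Model covariates will include patient demographics, biological sex, Elixhauser comorbidity index, and insurance payer". The Aim 1 text in the same section makes arm × period the main hypothesis. It also tests "a three-way interaction among study arm, time period, and implementation step", and lets step enter additively if that test is not significant. It includes nursing-unit random effects, and "All hypotheses will be two-sided at 5% significance level".

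On sample size, Section 8.1 says "we will randomly sample 1,520 hospitalizations divided equally between the four study groups and the baseline and follow-on periods" and "We will exclude the emergency department from Aim 3". Table 3 in Section 9.2 gives minimum detectable differences for the harmful rate of 0.220 to 0.486, "using a two-sided t-test for Poisson rates with 80% power at 5% significance level".

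The documents give no baseline harmful rate, mean stay, expected harmful-event count, sparse-data method or rule for non-convergence. Section 9.4.3, on secondary endpoints, covers only the qualitative interviews.

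**The concern.** A log-linear interaction test needs events in every cell it compares. The main test uses four arm × period cells; the three-way screen uses eight. When a cell is empty, the estimated log rate ratio is infinite and its Wald p-value goes towards 1. The likelihood-ratio statistic stays finite, but its chi-square reference is unreliable at such counts. An effective intervention makes this worse, because it empties the SAFE Loop follow-on cell.

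The outcome is patient harm. A finding of no significant effect could be read as absence of benefit, or of hazard, when the analysis could hardly have shown either. Nothing in the plan warns the reader, and Table 3 suggests the opposite.

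**Working it through.** **1. Reproduce the plan's tables.** The cluster-rate formula is (c − 1)d² = (1.96 + 0.8416)² × [(r0 + r1)/y + CV²(r0² + r1²)], with c = 10 units per arm without an implementation trend and c = 5 with one.

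- Table 1, from its stated inputs (2.26 with y = 7.362; 0.70 with y = 16.6): all 16 entries reproduce within 0.001.
- Table 3 states neither r0 nor y, so both were fitted with r1 = r0 − d. H3.2 gives r0 = 1.16, y = 38. H3.1 gives r0 = 5.95, y = 38. All 16 entries reproduce within 0.001. Example (no trend, CV 0.01): 9 × 0.22² = 0.436, against 7.849 × [2.10/38 + 0.0001 × 2.23] = 0.436.

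The fitted y equals the number of charts per unit-period: 1,520/(20 × 2) = 38. In thousands of patient-days, 38 charts supply only 38 × 4.86 to 6.01 days ÷ 1,000 = 0.18 to 0.23.

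**2. Exposure and events.** Section 1.1 gives 49,000 inpatient and 7,700 observation encounters, "resulting in a total of 294,470 patient-days of care in study nursing units per year". Removing the emergency department leaves 294,470 − 19,108 = 275,362 patient-days.

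| Assumed mean stay | Patient-days in 1,520 charts | Harmful events at 1.16 per 1,000 |
|---|---|---|
| 275,362/56,700 = 4.86 | 7,382 | 8.6 |
| 275,362/49,000 = 5.62 | 8,542 | 9.9 |
| 294,470/49,000 = 6.01 | 9,135 | 10.6 |

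**3. Empty cells.** With μ events spread evenly over m cells, P(at least one empty) = 1 − (1 − e^(−μ/m))^m.

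- Three-way model (m = 8, mean 1.07 to 1.24 per cell): 94–97%.
- Main model (m = 4, mean 2.1 to 2.5 per cell): 30–39% under no effect, and 45–55% if harm is halved in the SAFE Loop follow-on cell.
- At 6.01 days: 92% (m = 8) and 25% (m = 4, no effect).

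**4. Behaviour of the arm × period test.** These rates come from 200,000 simulated 2 × 2 Poisson tables per scenario, at 1.16 per 1,000 and 4.9 to 5.6 days, without overdispersion or unit random effects.

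| True effect on harm | Wald rejects | Likelihood ratio rejects |
|---|---|---|
| None | 0.2–0.4% | about 8.5% |
| Halved | 0.2–0.3% | 10–11% |
| Eliminated | 0% | 20–25% |

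Adding assumed patient covariates (600 simulated data sets, 9 events expected) changed little: 0.3% and 9.5% under no effect, about 0.5% and 10% if halved.

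**5. The other reading of Section 9.2.** The text equates a difference of 0.50 with 147 events and 116 harmful events avoided per year. Taken as a harmful share, 116/147 = 79%, and 0.79 × 5.95 = 4.7 per 1,000, or 35 to 43 events. Table 3's own rows imply 1.16/5.95 = 19%. At 4.7 per 1,000 the main test is close to nominal under no effect (Wald 4–5%, likelihood ratio 5–6%). Power for a halving is 12–15% (Wald) or 16–18% (likelihood ratio).

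**6. Against Table 3.** Halving 1.16 is a difference of 0.58, larger than every H3.2 entry (maximum 0.486), yet the test rejects at most about 11% of the time. Putting the real exposure into the plan's own formula gives no detectable reduction at all. For complete elimination at a 5.2-day stay (y = 0.198, CV term negligible), √[9 × 1.16²/(1.16/0.198)] − 1.96 ≈ −0.52, which is about 30% power.

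**7. Sensitivity to the assumed rate.** At 0.5 per 1,000 a main-test cell is empty in 81–87% of trials; at 2.0, in 6–10%.

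**The case against.** The event count is not documented. It combines a back-solved rate with an assumed stay, and the same fit needs an exposure that looks like a chart count, so the unit of the fitted rate is not secure either. The only harmful share that can be read from the text (116/147) leads to a test of nearly correct size. This stands: the count must be stated as an assumption, and the failure of test size is conditional on it. Low power is not, since it appears under both readings.

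Three stronger readings are tempting, and the documents support none of them.

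- A reader might infer that the main test usually meets an empty cell. That describes the three-way screen. The four-cell test meets one in a minority of trials under no effect, and the plan already falls back to an additive step when the screen is not significant.
- A reader might infer that H3.2 could never be significant even if all harm were removed. That holds for a Wald test with an empty cell at any sample size. The plan names no test, and the likelihood-ratio test rejects in 20–25% of trials under elimination at 1.16 per 1,000.
- A reader might blame the covariates. The adjusted simulations barely differ from the unadjusted ones.

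The simulations also omit the planned unit random effects, so they are not the exact planned model. With about 9 to 11 events over 19 units, that variance would be barely estimable.

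Finally, H3.2 is secondary, and the Aim 3 descriptive analysis already covers preventable adverse drug event rates and severity. That limits the weight of the point, but does not remove the formal 5% test or the 80% power printed for it.

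**Conclusion.** The point holds in conditional form. At 1.16 per 1,000 patient-days and a 4.9 to 5.6 day stay, the Aim 1 scheme does not deliver a 5% test of H3.2: it is far too conservative with Wald output and too liberal with a likelihood-ratio test. At about 4.7 per 1,000 the test size is acceptable. On neither reading does power to detect a halving of harm exceed about 18%, so the 80% power shown for differences of 0.22 to 0.49 is not supported by this sample. The size and power figures assume Poisson counts without overdispersion and leave out unit random effects. A null result on harm would be uninformative. This should be corrected, with weight appropriate to a secondary endpoint. It does not by itself require a change to the H3.1 model.

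**What to change.** In Section 9.4.2, take H3.2 out of the sentence that carries over the Aim 1 tests. For this outcome:

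- drop the step interaction and the patient covariates, which so few events cannot estimate usefully;
- report counts, patient-days and rates by arm and period;
- estimate the arm × period rate ratio with a small-sample method that keeps the change-from-baseline contrast and respects unit clustering. Examples are a unit-level permutation test within randomization blocks (allowing for the excluded emergency department) or a penalised Poisson interaction with unit effects. A follow-on-only ratio with plain Poisson intervals would meet neither requirement.

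In Sections 9.1, 9.2 and 9.4.2, state that H3.2 is exploratory, does not have 80% power, and that a null result is not evidence of no effect on harm. In Section 9.2, state the assumed harmful rate and mean stay, and reconcile Table 3 with the sentence on 147 and 116 events. Leave the H3.1 model unchanged for this point.

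The cost is SAP wording only. The downside is that H3.2 loses its standing as a confirmatory 5% test.
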